5. RANDOMIZATION

Survivors and their caregivers who meet the eligibility criteria, sign the informed consent form and complete all baseline assessments will immediately be randomized as a dyad to one of two trial arms by means of a computer-generated randomization table.

5.1 A total enrollment of 70 cancer survivors and their 70 primary caregivers is planned (70 dyads total, 35 dyads per trial arm).

5.2 The two trial arms will be as follows:

Trial Arm	Condition
1	Dyadic Exercise Intervention (EXCAP-PA) : Progressive walking and resistance exercise treatment, prescribed to both cancer survivors and their caregivers (daily walking and up to 7 times/week resistance prescription for 6 weeks). Cancer survivor and caregiver are also asked to discuss ways they can support one another in a) remaining adherent to exercise, and b) dealing with stress, including LGBT-specific minority stress.
2	Individual Exercise Intervention (EXCAP) : Progressive walking and resistance exercise treatment, prescribed solely to cancer survivors (daily walking and up to 7 times/week resistance prescription for 6 weeks). The caregiver is told not to change his/her exercise behavior in any way.

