6.4.5 **Physical function assessments.** Additionally, participants will be evaluated on **1)** body composition (bioelectrical impedance), **2)** heart rate variability, **3)** muscular strength (Handgrip Dynamometry, isokinetic knee flexion/ extension and shoulder diagonal), and **4)** aerobic capacity (6 minute walk test), in that order. All physiological fitness testing will be administered according to the Guidelines for Exercise Testing and Prescription (GETP) as outlined by the American College of Sports Medicine (ACSM). (See section 10.2 for additional details.)

6.4.6 Data from pedometers (or fitness trackers) and actigraphs will also be collected for analysis. Data from pedometers will be used to inform the walking prescription of the exercise interventions.

6.4.7 **Randomization.** Following completion of physical functioning assessments, dyads will be randomized to a trial arm. Instructions and an exercise kit for the home-based walking and progressive resistance exercise program will be given to survivors and caregivers together in Arm 1 and cancer survivors alone in Arm 2. Caregivers in Arm 2 will receive instructions and an exercise kit following the post-intervention assessment.

6.4.7.2 Cancer survivors and caregivers in dyads randomized to Arm 1 (EXCAP-PA) will each receive a home-based walking and progressive resistance exercise program to follow for a total duration of approximately 6 weeks. These dyads will be instructed in ways to use the exercise kits together. They will also meet briefly with a member of the study team, who will guide them through a discussion of barriers to exercise, ways they can support one another in remaining adherent to exercise, and ways of dealing with stress (including LGBT minority stress).

6.4.7.1 Cancer survivors in dyads randomized to Arm 2 (survivor-only EXCAP) will receive a home-based walking and progressive resistance exercise regimen to follow for a total duration of approximately 6 weeks. Caregivers in dyads randomized to Arm 2 will be told not to change their exercise behavior in any way, will not receive an exercise regimen to follow during the study period and will not discuss dyadic support with the cancer survivor.

6.5 **EXCAP:** Home-Based Walking and Progressive Resistance Exercise Program

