- 10.1.4 Quality of Life (QOL) will be assessed with the **Short Form Health Survey 12 (SF-12)**, a 12-item, multi-purpose scale designed primarily to measure functional health and well-being in a parsimonious fashion.⁶⁷ For the current study, mental and physical health summary scores will be used to assess QOL. Responses are anchored using a Likert scale ranging from 1 to 5 (strongly agree, agree, neutral, disagree, and strongly disagree, respectively). Cronbach’s Alpha coefficients indicate reliability of over .90.^{68,69}
- 10.1.5 Support between the patient and caregiver will be assessed with three measures: the Dyadic Adjustment Scale-7; the Dyadic Support Questionnaire; and the Social Provisions Scale.
- 10.1.5.1 The **Dyadic Adjustment Scale-7 (DAS-7)** is a 7-item scale designed to measure how individuals feel about their relationship with their caregivers using a unidimensional

global approach. Responses are anchored on a Likert scale ranging from 1 to 5 (strongly agree, agree, neutral, disagree, and strongly disagree, respectively). Cronbach's Alpha coefficients indicate an internal consistency range from .76 to .87, and a test-retest reliability range from .63 to .85 among cancer patients.⁷⁰

10.1.5.2 The **Dyadic Support Questionnaire (DSQ)** is an 18-item survey based on four functions of social support (emotional, appraisal, instrumental, and informational support). Nine items measure received social support, that is, support provided by the partner; nine additional items measure support provided to the partner. Items are anchored using a Likert scale ranging from 1 to 5 (from not at all to a great deal). Items are summed to create scales for received and provided support. Cronbach's alpha reliability coefficients range from .85 to .92, test-retest reliability coefficients range between .74 and .92 for this measure.⁷¹

10.1.5.3 The **Social Provisions Scale – Short Form (SPS)** is a 10-item survey designed to measure availability of emotional, tangible, and informational social support using a single general social support scale. Items are anchored on a four point Likert-type scale ranging from Strongly Disagree to Strongly Agree. Psychometric properties for the measure are excellent, with Cronbach's alpha reliability coefficients over .90.^{72,73}

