13. DATA ANALYSIS AND DATA MONITORING

13.1 Measures for the primary and secondary aims will be:

- 13.1.1 Cancer survivor's self-reported psychological distress (30 item POMS Total Score) at post-intervention (Primary Aim 1)
- 13.1.2 Cancer survivor's serum levels of stress-related biological endpoints (cortisol, serum amyloid A, C-reactive protein) at post-intervention (Secondary Aim 2)
- 13.1.3 Cancer survivor's received support from the caregiver (Dyadic Support Questionnaire) at post-intervention (Secondary Aim 3)
- 13.1.4 Cancer survivor's physical activity, as measured by actigraphy, at post-intervention (Secondary Aim 3)

13.2 Measures for the exploratory aim in caregivers will be:

- 13.2.1 Caregiver's self-reported psychological distress (30 item POMS Total Score) at post-intervention
- 13.2.2 Caregiver's serum levels of stress-related biological endpoints (cortisol, serum amyloid A, C-reactive protein) at post-intervention
- 13.2.3 Caregiver's received support from the cancer survivor (Dyadic Support Questionnaire) at post-intervention
- 13.2.4 Caregiver's physical activity, as measured by actigraphy, at post-intervention

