However, exploratory analyses will involve examining associations between outcomes of interest (distress and biological endpoints) and potential mechanistic factors (social support from a caregiver, adherence to the exercise intervention). Using the analysis techniques of Imai, I will evaluate whether change in social support and change in intervention adherence are associated with the effect of the intervention on psychological distress and biological endpoints linked with distress. This will involve generating a correlation matrix to test bivariate relationships. We will then conduct separate analyses for support and adherence with each outcome, using mixed effects ANCOVA models with arm, baseline distress or biomarker score, with/without support and adherence pre-post change scores as model predictor terms. We will also evaluate change in caregiver distress scores from baseline to post-intervention in the EXCAP-PA condition using paired sample t-tests, to examine whether caregivers benefit from supporting LGBT cancer survivors. We will also examine outcomes in L, G, B, and T subgroups and evaluate confounding and moderating factors. Because of the many exploratory analyses involved, any results will only be used for hypothesis generation.

13.3.3 Additional analyses will examine between group differences in the other outcome measures.

These will include: physical activity (ACLS, Daily Diaries), aerobic capacity (6 minute walk test), muscular strength (handgrip dynamometry, isokinetic strength test), depression (CES-D), anxiety (STAI), minority stress (Heterosexism and Identity Scale), relationship satisfaction (DAS-7), and quality of life (SF-12).

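### The Arm 1 caregiver test is meant to show benefit from supporting survivors, but those caregivers are also prescribed the exercise programme, so an improvement cannot be attributed to supporting

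*Combined protocol and SAP*

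**What the plan says.** **The test.** Section 13.3.3, in its paragraph on exploratory analyses, evaluates "change in caregiver distress scores from baseline to post-intervention in the EXCAP-PA condition using paired sample t-tests". The stated purpose is "to examine whether caregivers benefit from supporting LGBT cancer survivors".

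**What Arm 1 caregivers receive.** Section 5.2 describes the Arm 1 programme as "prescribed to both cancer survivors and their caregivers". Section 6.4.7 adds that Arm 1 survivors and caregivers "will each receive a home-based walking and progressive resistance exercise program to follow for a total duration of approximately 6 weeks". Under 6.6.1 and 6.7.1 the dyad also has a discussion of barriers, mutual support and stress, and joint weekly contacts.

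**What Arm 2 caregivers receive.** They are told to leave their exercise habits as they are. Section 6.4.7 says that they "will not receive an exercise regimen to follow during the study period and will not discuss dyadic support with the cancer survivor".

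**What the protocol expects of exercise.** Section 1.4 holds that exercise lowers distress by psychological and physiological routes. Section 1.5 (Study 3) reports a 7.24-point lower POMS Total for EXCAP against usual care in prostate cancer survivors.

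**The governing hypothesis and aim.** Section 2.1 hypothesises that caregivers gain from the partner-assisted intervention. Aim 2.5.1 compares EXCAP-PA with survivor-only EXCAP among caregivers. Neither singles out the act of supporting.

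**Measures.** On the Dyadic Support Questionnaire (10.1.5.2), nine items cover support received and "nine additional items measure support provided to the partner". The caregiver list in 13.2.3 names "Caregiver's received support from the cancer survivor (Dyadic Support Questionnaire) at post-intervention". Caregiver actigraphy is listed in 13.2.4.

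**The concern.** The purpose given for the test is narrower than what the arm delivers. An Arm 1 caregiver's distress may fall because of the caregiver's own walking and resistance training, because of the coached supporting role, or because of the study team's attention. Without a control group, time trend and regression to the mean can also contribute. The paired test responds to the sum of these.

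The protocol's own model predicts an improvement from exercise even if supporting has no effect. A significant result would therefore not bear on the question as worded. Section 13.3.1 says that the study is to inform a larger trial. A hypothesis that supporting helps caregivers, when the signal came from their own exercise, would point that trial at the wrong component.

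**Working it through.** **1. Can any planned contrast separate the components?**

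| Component | Arm 1 caregivers | Arm 2 caregivers |
|---|---|---|
| Prescribed exercise programme | yes | no |
| Coached support and stress discussion | yes | no |
| Joint weekly contact with survivor | yes | no |
| Informal support to the survivor | possible | possible |

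The first three rows change together. Within Arm 1 nothing varies by design. Between arms, exercise and coached support differ at once. A between-arm comparison removes time trend and regression to the mean, but it still estimates the package. The mechanism models in 13.3.3 concern support from a caregiver and exercise adherence as factors in the survivor outcomes. No caregiver model that adjusts for the caregiver's own activity is specified.

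**2. The plan's own power figure.** The only one is for survivors (13.5.1): 80% power for 6.90 points, SD 13.01, r = 0.7, 30 per arm, two-sided 0.05.
- ANCOVA residual SD = 13.01 × √(1 − 0.7²) = 9.29.
- SE of the difference = 9.29 × √(2/30) = 2.40; noncentrality = 6.90 / 2.40 = 2.88.
- Noncentral t with 57 df gives 80.7%, so the stated 80% is reproduced.

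No figure is given for the caregiver test.

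**3. Illustration for the caregiver paired test.** The inputs are 30 evaluable caregivers in the arm (4.1), and SD 13.01 and r = 0.7 borrowed from the survivors (13.5.1). The effect of supporting is set to zero. The effect of own exercise is set to 7.24 points (1.5, Study 3), half of that (3.62), 2 points or none.
- SD of change = 13.01 × √(2 × (1 − 0.7)) = 10.08.
- SE of the mean change = 10.08 / √30 = 1.84.
- Power is from the noncentral t with 29 df, two-sided 0.05.

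| Effect of own exercise (POMS points) | Chance of significance, r = 0.7 | r = 0.5 to 0.8 |
|---|---|---|
| 0 | 5% | – |
| 2 | 18% | 13–25% |
| 3.62 | 48% | 31–64% |
| 7.24 | 97% | 84–99.6% |

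**4. The same scenario between arms.** With residual SD 9.29, 30 caregivers per arm and no effect of supporting, an ANCOVA is significant 32% of the time at 3.62 points and 84% at 7.24. A control group therefore does not make the result specific to supporting.

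**The case against.** The strongest reply is that the documents already limit this analysis. Section 4.1 makes caregiver data exploratory. Section 13.3.3 opens by saying that the study is not designed or sized for mediation analysis, plans in general terms to look at confounders and moderators, and confines the results to hypothesis generation. Read with 2.1 and 2.5.1, supporting may be shorthand for the partner role as a whole. All of this stands, and it keeps the point small. It does not settle it: the general sentence names no confounder and no caregiver model, and the stated question remains narrower than the hypothesis and the aim.

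Four stronger readings are tempting, and the documents do not support them.

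- *Arm 2 caregivers give no support.* They lack the exercise regimen and the coached discussion, but nothing tells them to stop helping. Under 3.1 every caregiver is someone who helped during the cancer experience, and 13.3.2 compares dyadic support between arms.
- *Supporting goes unmeasured unless the caregiver's support-provided score is listed.* The survivor's received-support score (13.1.3) also reflects what the caregiver gives. Only the caregiver's own rating is unlisted.
- *The result is bound to be published as a benefit of supporting.* The percentages above are the power to detect an assumed exercise effect. They do not predict how anyone will word a conclusion.
- *The trial's main conclusions are at risk.* The primary and secondary aims concern survivors and do not use this test.

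**Conclusion.** The point holds as a mismatch between a stated question and the analysis meant to answer it. Coached support and prescribed exercise are bundled in Arm 1, so no specified analysis can attribute a caregiver improvement to supporting. That conclusion follows from the arm descriptions and needs no numerical assumption.

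The size is illustrative. With no effect of supporting, the paired test could be significant anywhere from 13% to 99.6% of the time, for own-exercise effects of 2 to 7.24 points and r from 0.5 to 0.8. This assumes that caregivers share the survivors' SD of 13.01, since the documents give no caregiver values. The 7.24 points come from prostate cancer survivors against usual care and may not carry over to caregivers.

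The consequence is limited to one exploratory analysis. The change is still worth making, because it alters what that analysis can be said to show.

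**What to change.** 1. **Reword the purpose in 13.3.3**: ask whether caregivers benefit from taking part in EXCAP-PA, meaning their own exercise plus supporting. This agrees with 2.1 and 2.5.1.
2. **Specify the analysis that aim 2.5.1 implies**: an ANCOVA of caregiver post-intervention POMS Total on arm and baseline POMS, reported as a mean difference with 95% CI. Under the borrowed planning values the half-width would be about 2.00 × 2.40 = 4.8 points. State that the estimate is for the package.
3. **Keep the Arm 1 pre-post change as descriptive**, with its 95% CI. Rewording alone would not be enough, because an uncontrolled paired test cannot answer the package question either.
4. **Optional**: report the association of caregiver POMS with the caregiver's own support-provided score and own activity (actigraphy), with 95% CI, labelled descriptive and non-causal. Within Arm 1 there are about 30 caregivers, and these non-randomised predictors are probably correlated, so precision will be low.

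The cost is a few sentences and one model on data already being collected. There are no new visits or measures, and the survivor analyses do not change.

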13.4 Missing Data

13.4.1 We expect some attrition due to loss to follow up, declining follow up, or illness. We expect to retain 85% of the sample over the short 6 week period from pre- to post-intervention. This estimate is conservative, as a previous study of LGBT patients and partners retained 93% of a sample of 249 dyads after 15 months and [name] retained 100% of participants in his feasibility trial. With 85% retention, recruitment of 70 LGBT survivors will mean that we will have a sample of 60 survivors (and 60 caregivers) at the post-intervention assessment.

[figure not shown]
13.4.1 In the event that a participant willingly withdraws or is removed from the study by the investigator, any data already collected will be analyzed as deemed appropriate, unless the participant asks to have his or her data removed from the study. If a survivor or caregiver withdraws or is removed from the study following the baseline assessment, his/her partner may continue in the study.

13.4.2 Every effort will be made to encourage and facilitate provision of questionnaire and biological data. In the event of missing data, we will use intent-to-treat analyses and evaluate missing at random and missing not-at-random assumptions (MAR/MNAR) to determine the impact on results. We anticipate using multiple imputation if data are MAR and pattern-mixture models if data are MNAR.

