7. SUBJECT CONSENT AND WITHDRAWAL

- 7.1 Current, state, federal, and institutional regulations concerning informed consent will be followed. Participation in this study is voluntary. Participants are free not to take part or to withdraw at any time, for whatever reason, without risking loss of present or future care they would otherwise expect to receive. In the event that a patient does withdraw from the study, the information they have already provided will be kept in a confidential manner. Participants may discontinue participation in the study at any time if they decide they do not wish to take part any longer. Participants may be withdrawn from the study by research personnel if it is deemed in their best interest to no longer participate.

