- 9.1.3 In terms of emotional distress, the quantitative assessments explore issues associated with the relationship between survivors and caregivers, feelings about treatment, and mental health. The sensitive nature of these items may cause participants to become distressed as they think about their responses. Specific to research with dyads, during the intervention or possibly as a result of responding to questionnaire items, issues may arise that could lead to tension between survivor and caregiver and possible conflict and/or violence within the dyad.
- 9.1.4 In terms of loss of confidentiality, both quantitative data and biological samples from participants will need to be stored. Though rigorous and well-tested data safety and security guidelines will be observed, there is still a chance that confidentiality could be breached and sensitive medical information could become known to persons outside the research team.
- 9.2 ***Adequacy of protection against risk:*** Four potential risks have been associated with participation in this study: 1) physical harm associated with assessment procedures, 2) physical harm associated with

intervention procedures, 3) emotional distress and 4) loss of confidentiality.

- 9.2.1 Physical harm associated with assessment and intervention procedures: Every effort will be made to minimize the risks associated with study procedures for all participants. First, all participants (cancer survivors and caregivers) must have the approval of their physician to enter the study. All testing and exercise prescription discussions will be supervised by an American College of Sports Medicine (ACSM) Certified Exercise PhysiologistSM. A physician (or physician's designee) will be present when necessary according to ACSM Guidelines; for example, in circumstances where the participants' physician has approved the participant to participate in the study, but review of a participant's medical history reveals cardiorespiratory, orthopedic, or central nervous system conditions that do not preclude participation in exercise but might increase the participant's risk of complications during fitness testing. This conservative policy is designed to ensure the safety and minimize the risk to cancer survivors. EXCAP uses standardized guidelines for exercise testing and prescription provided by the ACSM, which have been shown to be safe to use with medically ill populations.

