10.2.1.2 The **Aerobic Center Longitudinal Study Physical Activity Questionnaire (ACLS)** is a measurement instrument that includes assessment of lifestyle physical activity.⁸⁹ The questionnaire requests that participants report their engagement in fourteen different physical activities (frequency, intensity and duration) over the last three months. Estimates of energy expenditure are calculated using the following equation: (sessions/week) * (min/session) * (hour/min) * MET [Note: MET = metabolic energy expenditure rate] for each activity and then summed to provide total MET hours of energy expenditure for a week. The index of walking, jogging, and running predicted treadmill performance time ($\beta = .31$) and there is a moderate relationship between energy expenditure estimates and treadmill performance ($r = .41$).

10.2.1.2 The **Daily Diary (as referenced elsewhere in the protocol)** is designed to track daily physical activity. The participant will be asked to complete the journal each night immediately prior to sleeping and record steps walked, minutes of resistance training completed, and a Rating of Perceived Exertion. The daily diary will also include an item assessing average daily distress, rated on a 0-10 scale. All participants will complete this daily assessment of distress, but only those randomized to the exercise condition will complete the exercise-relevant measures.

10.2.1.3 **Actigraphy**, as an objective measure of physical activity, will involve the waist-worn actigraph. The actigraph provides calculated energy expenditure values for Active Energy Expenditure (AEE) in kilocalories and total energy expenditure in Metabolic Equivalents per Time (METs) in kilocalories/min/kg. The actigraph features a variable epoch length which can be set between 1 to 240 seconds and 16 MB non-volatile memory. “Non-volatile” means that even if the battery, which can log 4000 hours of runtime, becomes exhausted, the data remain intact. The actigraph AEE Algorithm is based on validation studies, copies of which are available upon request. Software supplied by the manufacturer will be used to determine bouts of moderate or higher activity during each assessment period (day -7 to day 0, day 35 to day 42).

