11. CONFIDENTIALITY OF DATA AND DATA STORAGE

11.1 Data Collection Table

FORM	Baseline	Post Intervention
On Study Data (Demographic and clinical data)	X	
Clinical Record Information (Clinical data – survivor only)	X	
Medication Form	X	
Physical Activity Readiness Questionnaire (PAR-Q+)	X	
Profile of Mood States (POMS)	X	X
Aerobic Center Longitudinal Study Physical Activity Questionnaire (ACLS; 15-item physical activity history measure)	X	X
Patient Health Questionnaire - 9 (PHQ-9)	X	X
Spielberger State/Trait Anxiety Inventory (STAI Form Y-1)	X	X
Short Form Health Survey 12 (SF-12)	X	X
Dyadic Adjustment Scale – 7 (DAS-7)	X	X
Dyadic Support Questionnaire (DSQ)	X	X
PROMIS Patient-Reported Item Batteries	X	X
Insomnia Severity Index (ISI)	X	X
Multidimensional Fatigue Symptom Inventory (MFSI)	X	X
Heterosexism and Identity Questionnaire	X	X
Physician Interaction (PEPPI, THC, and SSE) Scales	X	X
Physiological Fitness Test Evaluations (6 min walk test, handgrip dynamometry, isokinetic strength test, bioelectrical impedance)	X	X
Heart Rate Variability (Firstbeat Bodyguard 2)	X	X
Biological Endpoints (via blood draw)	X	X
Pedometer (or fitness tracker)	Continuous (for those exercising)	Continuous (for those exercising)
Actigraphy	7 days before	7 days before
Daily Diary	Continuous (for those exercising)	Continuous (for those exercising)

- 11.2 All hardcopy research records will be stored onsite in the University of Rochester Medical Center, in the Cancer Control Unit and the PEAK Lab of the James P. Wilmot Cancer Institute. The Cancer Control Unit is located in the Saunders Research Building, in an office suite secured by electronic key cards. The PEAK Lab is located in the medical center and is also secured by electronic key cards. Offices within the Unit and the Lab are again secured by key and data is kept in locked file cabinets. Electronic research records are stored on the University of Rochester Medical Center's password secured and

Protocol date: 7/06/2020

firewall protected networks. These are the same methods of security used for patient medical records. Human serum samples are stored in locked freezers, within locked and alarmed laboratories that are accessible by key codes and electronic card swipes. All study data will be kept for a period of at least 6 years after the study and all reports and publications are complete.

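### Section 13.4.2 ties the missing-data method to whether data are MAR or MNAR, which one pre and one post POMS cannot settle, and it does not plan to use survivors' daily distress ratings in the imputation

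*Combined protocol and SAP*

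**What the plan says.** - **Method (13.4.2).** Missing data will be handled by intent-to-treat analysis, with MAR and MNAR assumptions evaluated for their effect on the results. The next sentence is "We anticipate using multiple imputation if data are MAR and pattern-mixture models if data are MNAR". No imputation variables, MNAR shift or basis for choosing between the two are given.
- **Expected loss (13.4.1).** "We expect some attrition due to loss to follow up, declining follow up, or illness". Retention is put at 85%, so 70 survivors become about 60. The plan calls this conservative and cites 93% in an earlier dyad study and 100% in the feasibility trial. If one dyad member leaves, "his/her partner may continue in the study".
- **Withdrawal (7.1).** The text covers the right to leave and removal by staff. For data in hand it says that "the information they have already provided will be kept in a confidential manner". It does not say that the reason for leaving is recorded, and Table 11.1 lists no off-study form.
- **Daily diary (10.2.1, Daily Diary item).** "The daily diary will also include an item assessing average daily distress, rated on a 0-10 scale". That item has all participants give the rating. Table 11.1 marks the diary "Continuous (for those exercising". Survivors exercise in both arms, so all 70 are covered under either text.
- **Use of the diary in the analysis.** The second item numbered 13.3.3 lists it only under "physical activity (ACLS, Daily Diaries".
- **Dyad risk (9.1.3).** "issues may arise that could lead to tension between survivor and caregiver and possible conflict and/or violence within the dyad".

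**The concern.** MAR and MNAR differ in how missingness relates to the value that was not observed. With a single post-intervention POMS, that value is absent for exactly the people in question. A rule that selects multiple imputation or pattern-mixture modelling according to which assumption is true therefore has nothing to operate on. If it is applied literally, the choice is a judgement made once the data are in hand.

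The survivors without a post score may be more distressed than their baseline predicts. If this is so in one arm only, imputing from baseline makes that arm look better than it is. The direction depends on which arm loses them. Section 13.3.1 intends the estimated effect size to inform a Phase III trial, so even a modest distortion would carry forward.

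The daily distress rating is the obvious partial remedy. It measures distress between the two POMS assessments and is already being collected. For someone who leaves in week 3 it holds information that baseline does not. The plan assigns it no role in the imputation.

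**Working it through.** **Inputs.** SD 13.01, baseline-to-post correlation 0.7, target difference 6.90, 80% power and the 0.05 level come from 13.5.1. The two-sided test and 30 evaluable survivors per arm come from 13.3.1. The 35 randomized per arm come from 4.1 and 5.1, and 85% retention from 4.1 and 13.4.1. The excess distress of leavers is an assumption, since the documents give none.

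**1. Reproduce the plan's power.** The ANCOVA residual SD is 13.01 × √(1 − 0.7²) = 9.29. The standard error of the arm difference is 9.29 × √(2/30) = 2.40. The noncentral t with 57 df gives 80.7% power for 6.90, and 80% power at 6.84. The stated 80% for 6.90 reproduces.

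**2. Number missing.** 70 × 0.85 = 59.5, about 60, so about 10 survivors (5 of 35 per arm) lack the primary outcome.

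**3. Bias if the excess is in one arm only.** Let k survivors be missing in that arm, with true post scores δ points worse than predicted from baseline. Bias = (k/35) × δ. The rejection rate under no true difference uses the same SE and df as step 1.

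| k of 35 | δ (assumed) | Bias | Share of 6.90 | Two-sided rejection rate |
|---|---|---|---|---|
| 5 | 4.65 (half a residual SD) | 0.66 | 10% | 5.9% |
| 5 | 9.29 (one residual SD) | 1.33 | 19% | 8.5% |
| 5 | 13.01 (one raw SD) | 1.86 | 27% | 11.9% |
| 8 | 9.29 | 2.12 | 31% | 14.0% |

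**4. Bias if the excess is the same in both arms.** Bias = δ × (k₁ − k₂)/35. At 5 versus 5 it is 0. At 7 versus 3 it is (4/35) × δ, or 0.53 to 1.49 points for δ from 4.65 to 13.01.

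**5. Better retention.** At 93%, 35 × 0.07 = 2.45, so 2 or 3 are missing per arm. With δ = 9.29 in one arm only, the bias is 0.53 to 0.80 points (8% to 12% of 6.90).

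**6. What the diary could recover.** This was simulated with 35 per arm, 5 versus 5 missing, exits in one arm averaging one residual SD of excess distress and exits in the other arm random. The diary-POMS correlations given baseline are assumptions.
- Leaving follows recorded diary distress (partial correlation 0.7): bias falls from 1.29 to 0.03.
- Leaving follows distress the diary only partly captures: bias falls from about 1.3 to 1.19, 1.04 and 0.66 at partial correlations of 0.3, 0.5 and 0.7.

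**7. How the diary must be entered.** Averaging each person's last seven recorded days compares an early week for leavers with a late week for completers. In simulations where exits follow early diary distress and early and late ratings correlate 0.7, that summary overcorrects: 0.75 becomes 0.27 in the opposite direction in one set-up, and 0.99 becomes 0.44 in the opposite direction in another. Means aligned by study week remove the bias when leaving follows recorded distress.

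**The case against.** The strongest reply is that 13.4.2 already commits to evaluating both assumptions for their effect on the results. This reads naturally as sensitivity analysis, and the sentence naming the two methods is worded as an expectation rather than a rule. A reader might infer that the plan has no sensitivity analysis at all; the text does not support that. What remains is that the second sentence still attaches each method to a state of the data that cannot be observed. Under either reading there is no shift, no imputation variable and no statement of which analysis leads.

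The plan also does not say that imputation would use baseline POMS alone. Baseline includes the PHQ-9, STAI, SF-12 and DSQ, and 11.3 and 13.4.1 allow collected data to be analysed as appropriate. So the diary is unassigned, not excluded. The figures in step 3 describe imputation that adds nothing beyond baseline POMS.

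A reader might further infer that dyad conflict will drive distressed survivors out of Arm 1 and bias the trial in a known direction. Section 9.1.3 is a general risk statement. Differential loss is plausible because the Arm 1 weekly calls involve both members, but nothing in the documents shows that it will occur.

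Nor does the lack of a withdrawal or adverse-event table by arm in section 13 show that exits and events go unrecorded. The serious adverse event window in 8.2.2 depends on the off-study date. Weekly contact (6.7.1) gives staff a route to the reason for leaving, and section 8 provides grading and committee review. Those tables are a matter of reporting detail and do not decide between MAR and MNAR.

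**Conclusion.** The point holds as a low-severity improvement. The stated rule conditions on something the POMS data cannot reveal, and a relevant measure collected from every survivor has no planned role in the imputation. The bias of 0.66 to 1.86 points rests on three assumptions: 85% retention, excess distress of 4.65 to 13.01 points among leavers, and that excess confined to one arm. If the excess is equal with 5 missing in each arm, the bias is zero. At the retention seen in earlier studies it would be small or absent. The documents do not support a claim that the primary result will be biased, or in which direction. They support only that the plan does not fix in advance how it would find out.

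**What to change.** Rewrite the method in 13.4.2 as follows.

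1. **Main missing-data analysis.** Use multiple imputation under MAR for all 70 randomized survivors. The imputation variables are arm, baseline POMS and mean diary distress by study week (week 1, week 2 and so on), with later missing weeks imputed from earlier ones. Do not use the last seven recorded days.
2. **Sensitivity analysis, always run.** Use a delta-adjusted pattern-mixture analysis that adds 0 to 13 points to the imputed scores of every survivor with a missing post score, varied separately by arm. Apply it to all of them, not to a subgroup defined by reason: illness is an expected cause of loss, people lost to follow-up give no reason, and with about 5 missing per arm a subgroup may be one or two people.
3. **Exit log.** Record date and reason of exit for each dyad member to help interpret step 2. Section 4.1 plans for 140 enrolled and 120 evaluable, so this is about 140 − 120 = 20 short entries.

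The cost is one revised paragraph, the log and a little more analysis, with no new participant assessments. Three limits remain. The diary ends when a person stops completing it, and it removes only part of the bias when leaving depends on distress it does not capture. Recorded reasons inform the MAR judgement but cannot prove it. The 0 to 13 range, up to about one SD, is a judgement to be set before the outcome data are seen.
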